Specific Aim 1: To measure the effects of respiratory training on respiratory and voice outcomes in patients with presbyphonia. Hypothesis 1: The respiratory training groups (inspiratory and/or expiratory) will demonstrate greater improvement in respiratory outcomes, measured through pulmonary function tests and respiratory pressure measures, compared with the voice exercises-only group. Hypothesis 2: The respiratory training groups (inspiratory and/or expiratory) will demonstrate greater improvement in voice-related outcomes than the voice exercises-only group.

Secondary Aim 1: To assess the reliability of the ratings for subjective outcomes (videostroboscopy ratings and perceptual judgements of voice quality). Hypothesis 1: Intra-judge reliability will be of at least 80%. Hypothesis 2: Inter-judge reliability will be of at least 70%.

Specific Aim 2: To determine how baseline measures of respiratory function influence the effects of respiratory training (respiratory and voice outcomes). Hypothesis 1: inspiratory training will have maximal effect on patients with decreased maximum inspiratory pressure (MIP). Hypothesis 2: Expiratory will have maximal effect on patients with decreased maximum expiratory pressure (MEP).

This is an initial feasibility and mechanistic study that has the potential to reveal that respiratory training can significantly improve outcomes from voice therapy by acting in synergy with voice exercises. Currently,

much time is spent in voice therapy on subthreshold 'breathing exercises' that lack evidence. This project will provide guidance for evidence-based and theory driven approaches to leverage respiratory function to improve voice therapy. Conversely, negative findings from this study would indicate that respiratory function is ineffective and not a viable target for therapy in this patient population.

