6.0 Number of Subjects

Forty-eight patients-participants and up to six raters-participants will be recruited for the study.

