Raters will rate the audio recordings with the CAPE-V form and the videostroboscopy images with the VALI form. They will rate pre- and post-intervention de-identified recordings for each participant, and an additional sampling of 20% of the recordings (for intrarater reliability testing).

Data Collection

Data collected will be the same for Aim 1 and Aim 2. It will include information in the patient's medical record (obtained from standard of care assessment) and obtained through a demographic questionnaire as well as clinical data using standardized collection instruments: spirometry measures, muscle pressure measures and acoustic assessment.

Each video and audio recording will be de-identified when videos are converted into .mpg, .nsp or .mp3 files before distributing the recordings via Box for analysis. Participant raters will review the de-identified digitized recordings for the purposes of data collection and score each video and audio recording using the VALI and CAPE-V rating forms, respectively.

Spirometry, muscle pressure data, and voice data will be recorded in a data collection sheet by the study team member. Data collection sheets will be labeled with the alphanumeric identifier of the patient-participant. Completed data collection sheets, with ratings from the CAPE-V and VALI, will be entered in the database by a study team member. Research records will be retained for a period of six years to allow evaluation and repetition of the results by others.

Study personnel will enter mandatory data fields for demographics according to the NIH minimum standards for maintaining, collecting and presenting data on gender, race and ethnicity. The demographic and clinical data will be exported for analysis.

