12.0 Data Management

Data Analysis Plan

Demographic characteristics will be compared across the 3 intervention groups, using a RxC contingency table method for categorical variables (gender, smoking history, voice use, racial and ethnic category) and a one-way ANOVA for continuous variables (age, weight, height). Baseline characteristics will be compared across the 3 intervention groups using a Kruskal-Wallis one-way analysis of variance by ranks for ordinal data (GFI, RSI, and VHI scores), a RxC contingency table for categorical variables (glottal gap shape, free edge contour, vertical level, phase closure) and a one-way ANOVA for continuous variables. Aim 1: To assess the effects of respiratory training on voice and respiratory outcomes in patients with presbyphonia. Data will be analyzed on an intention-to-treat basis using multifactor repeated measures generalized linear regression. Distributional assessment will be made for each outcome to confirm optimal distributional assignment and potential need for outcome transformation (i.e. log link). In the model, the repeated factor is time, which has two levels (pre- or post-intervention) and the independent factor is the intervention, which has three levels (IMST, EMST, VFE). In the case of a significant between-subjects effect, multiple comparison tests will be conducted to determine which groups differ. The post-hoc analysis will be done using Tukey's honestly significant difference (offering protection against type I error without being too conservative). Spearman and Person correlations will be calculated to establish inter and intrarater reliability. Aim 2: To identify profiles of presbyphonic patients that would benefit the most from respiratory training. Logistic regression will be conducted to predict which patients improved following inspiratory training and which patients improved following expiratory training, based on their baseline clinical characteristics. Two outcome variables will be indicative of meaningful clinical improvement: 1) MPT (to measure function), and 2) GFI (to measure patient perception of function). Meaningful clinical improvement will be defined by an increase of at least 4 seconds in MPT or a decrease of at least 4 points in GFI score. Participants will be dichotomized as having meaningful clinical improvement, or not, based on these outcomes. Predictors will include MIP, MEP, maximum SPL, breaths per minute, FVC, FEV1, and P_s. These measures were chosen because they are directly influenced by the integrity of the respiratory system.

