Unknown risks: Respiratory training has never been tested on patients with presbyphonia. The results of this combination are unknown. Although unlikely, there is a slight risk that unforeseen adverse events could result from this combination.

Protections Against Risk

Loss of confidentiality: Protection against the loss of confidentiality will be diminished by 1) completing study aims at one data collection site, 2) minimizing the participants involved to only those needed to accomplish the study aims (see sample size justification above), 3) de-identifying data at the earliest opportunity, and 4) maintaining stored data in locked/password protected locations whose access is restricted to members of the study team. All data collection and study activities will be conducted at MUSC. The patient subject sample will include up to 48 patients referred for a videostroboscopy within the scope of their usual care at MUSC and who meet the inclusion criteria. The sample will be limited to the MUSC site because historical accruals have been shown sufficient to meet power (see participant section above). Six participant raters will be recruited from SLPs who have experience with voice disorders. An alphanumeric identifier will be used instead of patient participant name and rater participant name at the earliest possibility. In order to ensure participant's confidentiality, database entry will be password protected and study documents will be maintained in a locked cabinet in the PIs locked office. Patient identity will also be protected by confidentiality policies and procedures already in place at the MUSC site. A participant may withdraw from the study at any time without penalty or prejudice.

Spirometry and muscle pressure testing: If the patient-participant manifests signs of discomfort or dizziness, the spirometry or muscle pressure testing maneuver will be interrupted following the American Thoracic Society's (ATS) recommendations(47). Stopping the maneuver will avoid a syncope, which could follow due to the interruption of venous return to the thorax during prolonged exhalation. As a precaution, all assessments will be done in a sitting position, in a chair with arms and without wheels to prevent falls.

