16.0 Potential Benefits to Subjects or Others

The experimental groups may benefit from receiving a respiratory training intervention. Respiratory training directly targets the respiratory system and *could* lead to greater improvements in both respiratory and voice outcomes than those observed with voice therapy alone.

There is a possibility that the participant will not directly benefit from being part of this research project.

For the subjects of the study, as well as for future voice patients who could benefit from this intervention if it were to be proven effective and to be implemented in common usual care, it could lead to important benefits:

- Improved respiratory and voice outcomes;
- Greater improvements in a person's daily activities involving communication;
- Reduced number of voice therapy sessions needed
- Improved voice-related quality of life

Because communication is a social activity, these benefits are also susceptible to impact the quality of life of the participants' significant other, family and caregiver.

The minimal risks associated with this research project are reasonable in relation to the potential benefits to the study participants and others. In the case where the intervention is not shown to be more efficacious than voice therapy only, the subjects would still receive the benefits from standard of care voice therapy.

Participant-raters will be compensated at a rate of \$40 for every 10-rating package (one package includes an endoscopy recording and an audio file). It is estimated that each rater will rate a total of 39 packages, for a total of \$160 for their participation in the study.

Both patient participants and participant raters may indirectly benefit, along with other patients, clinicians and society from the dissemination and implementation of the results of this research. The results of this research if in-line with our pilot data, will provide evidence that will serve as a guide for speech-language pathologists to inform patient management decisions. In general, any study that improves the effectiveness of voice intervention and the evidence upon which treatment recommendations are based may improve the health status and quality of life of patients and decrease the economic burden of voice disorders. These benefits outweigh the minimal risks that may result from loss of confidentiality and discomforts associated with the respiratory training interventions.

Importance of the Knowledge to be Gained

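### The implied 6 to 7 repeat ratings per judge are too few for a per-judge correlation to assess the 80% intra-judge target, and the plan does not say how judges are combined

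*Combined protocol and SAP*

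**What the plan says.** Section 1.0, Secondary Aim 1, states the hypothesis "Intra-judge reliability will be of at least 80" per cent, for videostroboscopy ratings and perceptual judgements of voice quality. The index is not defined there.

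Section 10.0 (Rater Participants) says of the raters: "They will rate pre- and post-intervention de-identified recordings for each participant", plus "an additional sampling of 20% of the recordings (for intrarater reliability testing"). It does not say whether the 20% is of each rater's own recordings or of all recordings, nor whether every rater sees every recording.

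Section 16.0 adds a workload: "It is estimated that each rater will rate a total of 39 packages", where "one package includes an endoscopy recording and an audio file". Section 6.0 allows up to six raters; Section 15.0 says "Six participant raters will be recruited from SLPs who have experience with voice disorders".

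The analysis in Section 12.0 is one sentence: "Spearman and Person correlations will be calculated to establish inter and intrarater reliability". It gives no confidence interval, decision rule or method for combining raters. The sample size justification is built on maximum phonation time and does not address reliability.

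**The concern.** A hypothesis with a numerical target needs an estimate precise enough to be compared with it. The plan does not state the number of repeat pairs per judge, and the figure implied by the workload is very small. A correlation for each judge would then say little about that judge. An analyst who sees this may merge the raw pairs of all judges, which the plan neither prescribes nor excludes; differences in severity between judges would then count as true variation between recordings. At stake is the answer to Secondary Aim 1, Hypothesis 1, and what readers can be told about the consistency of the CAPE-V and VALI ratings listed as voice measures in Section 4.0. Changing the index alone would not help: an ICC computed judge by judge on the same few pairs would be about as imprecise.

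**Working it through.** **Inputs.** 48 patients and up to six raters (Section 6.0); two recordings per patient and 20% repeats (Section 10.0); 39 packages per rater, one video and one audio file each (Section 16.0); target 0.80 (Section 1.0). The documents give no confidence level for reliability; I assume 95% two-sided.

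**Reproducing the 39 packages.**
- Recordings: 48 × 2 = 96.
- With six raters and two raters per recording (my inference): 96 × 2 / 6 = 32 per rater.
- Adding 20% of the rater's own share: 32 × 1.2 = 38.4, which rounds up to 39.
- Repeats per rater: 39 − 39/1.2 = 6.5, so 6 to 7.
- The pay in Section 16.0 agrees with this workload: $40 per 10 packages × 3.9 = $156, against the stated $160.

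**Literal reading of Section 10.0.** If every rater rates everything, 96 × 1.2 = 115.2 packages, with 0.2 × 96 = 19.2 repeats. That contradicts the 39, and the pay would be about $40 × 11.5 = $460. A different split also gives 38.4: five raters, each recording rated once (19.2 each), and all raters repeating 20% of the whole set (19.2). So 19 repeats per judge cannot be excluded.

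**Precision per judge.** 95% CI = tanh(atanh(r) ± 1.96/√(n − 3)), at observed r = 0.80:

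| Repeat pairs | 95% CI |
|---|---|
| 6 | −0.03 to 0.98 |
| 7 | 0.12 to 0.97 |
| 19 | 0.54 to 0.92 |

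For the lower bound to exceed 0.80, the observed r must be above 0.977 (6 pairs), 0.969 (7) or 0.920 (19).

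**Classification by a point-estimate rule.** Simulated probability of Pearson r ≥ 0.80 with bivariate normal ratings:

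| True r | 7 pairs | 19 pairs |
|---|---|---|
| 0.60 | 23% | 6% |
| 0.70 | 37% | 19% |
| 0.90 | 85% | 95% |

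With 7 pairs the rule passes 37% of judges at true 0.70 and fails 15% at true 0.90. For Spearman the corresponding figures are 28% and 33%.

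**Raw pooling over judges.** Let ρ be the true within-rater reliability and v the between-rater variance divided by the within-rater rating variance. The pooled correlation tends to (ρ + v)/(1 + v). If rater variance is f times the subject variance, v = fρ. At ρ = 0.70 and f = 0.5, v = 0.35 and the limit is 1.05/1.35 = 0.78. Simulation with six raters × 7 pairs at ρ = 0.70:

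| f (assumed) | Mean pooled r | Share of trials ≥ 0.80 |
|---|---|---|
| 0 | 0.70 | 8% |
| 0.25 | 0.73 | 19% |
| 0.5 | 0.76 | 33% |
| 1 | 0.80 | 56% |

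A within-rater ICC from the same data averages 0.69 and reaches 0.80 in 7 to 8% of trials, whatever f is. The bias can also run the other way: if each rater shifts by a different amount between sessions (shift variance 0.25 of the rating variance), a true 0.80 falls to 0.80/√1.25 = 0.72 when pooled.

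**All repeat pairs used within raters.** About 39 to 42 pairs (6 × 6.5 to 6 × 7). The Fisher interval at 0.80 with 39 pairs is 0.65 to 0.89; simulated within-rater ICCs at true 0.80 with 6 × 7 pairs fall between 0.65 and 0.89 in 95% of trials. Averaging the six within-rater correlations on the Fisher scale gives 0.60 to 0.90 with 7 pairs each.

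**The case against.** The strongest reply is that 6 to 7 is nowhere stated. It is worked back from an estimated workload in a compensation paragraph, and the design section read literally gives 19. That stands, and it makes the mismatch between Sections 10.0 and 16.0 part of the point. It does not remove the problem, since the interval with 19 pairs still runs from 0.54 to 0.92.

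A reader might infer that the verdict on each judge is a coin flip, because a judge whose true r is exactly 0.80 passes about 57% of the time with 7 pairs. That is no evidence about sample size: at the threshold the probability is still about 53% with 40 pairs and 51% with 400. Only results away from the threshold count. Nor does the plan state a pass/fail rule per judge; the rule above only illustrates the imprecision.

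A reader might also infer that pooling would inflate the result. The documents do not plan pooling, and Section 10.0 calls the judges trained. Inflation needs severity differences, vanishes without them, and is reversed by rater-specific drift.

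It is also fair that averaging within-rater correlations would fit the present wording and avoid raw pooling. The plan does not say so, however, and a correlation ignores a judge's systematic shift between sessions.

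Finally, no Aim 1 analysis depends on the reliability result, and the outcomes used for sample size and Aim 2 (phonation time, GFI) are not scored by the raters.

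**Conclusion.** The concern holds in a limited form. On the documents' own workload, and if the 20% applies to each rater's own share, each judge supplies about 6 to 7 repeat pairs. A per-judge correlation at that size is too imprecise to assess the 80% target at plausible reliabilities, and 19 pairs would still leave a wide interval. This is not an absolute impossibility: an observed r above about 0.97 with 7 pairs would clear 0.80.

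Inflation from pooling is a possibility that the plan leaves open. Its size (a true 0.70 appearing as 0.70 to 0.80 on average) rests on assumed rater variances between zero and the subject variance.

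The consequence is confined to a secondary aim. The documents do not support reading it as a threat to the Aim 1 comparisons, and they do not support the view that a better index alone would make the target decisively testable.

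**What to change.** 1. Reconcile Sections 10.0 and 16.0: state how many raters score each recording, what the 20% is taken from, and the resulting repeats per rater.
2. In Section 12.0, replace the intra-rater correlations with one within-rater ICC per continuous or ordinal scale, estimated from all repeat pairs in a model with rater and recording terms, so that severity differences between raters are removed. For nominal VALI items, use a kappa combined within raters. Give each with a 95% CI.
3. State that the 80% target is assessed for the rater panel on that estimate and its CI, and that per-judge values are descriptive.

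The cost is a few sentences and one model per scale, with no extra ratings. The downside is that individual judges receive no verdict and the interval stays wide, about 0.65 to 0.89 around 0.80, so the target may be neither confirmed nor refuted. For scale: by the Fisher approximation, 80% power to put the lower bound above 0.80 when the true r is 0.90 needs about 48 (one-sided 5%) to 60 (two-sided 5%) repeat pairs, more than the 39 to 42 implied.

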12.0 Data Management

Data Analysis Plan

Demographic characteristics will be compared across the 3 intervention groups, using a RxC contingency table method for categorical variables (gender, smoking history, voice use, racial and ethnic category) and a one-way ANOVA for continuous variables (age, weight, height). Baseline characteristics will be compared across the 3 intervention groups using a Kruskal-Wallis one-way analysis of variance by ranks for ordinal data (GFI, RSI, and VHI scores), a RxC contingency table for categorical variables (glottal gap shape, free edge contour, vertical level, phase closure) and a one-way ANOVA for continuous variables. Aim 1: To assess the effects of respiratory training on voice and respiratory outcomes in patients with presbyphonia. Data will be analyzed on an intention-to-treat basis using multifactor repeated measures generalized linear regression. Distributional assessment will be made for each outcome to confirm optimal distributional assignment and potential need for outcome transformation (i.e. log link). In the model, the repeated factor is time, which has two levels (pre- or post-intervention) and the independent factor is the intervention, which has three levels (IMST, EMST, VFE). In the case of a significant between-subjects effect, multiple comparison tests will be conducted to determine which groups differ. The post-hoc analysis will be done using Tukey's honestly significant difference (offering protection against type I error without being too conservative). Spearman and Person correlations will be calculated to establish inter and intrarater reliability. Aim 2: To identify profiles of presbyphonic patients that would benefit the most from respiratory training. Logistic regression will be conducted to predict which patients improved following inspiratory training and which patients improved following expiratory training, based on their baseline clinical characteristics. Two outcome variables will be indicative of meaningful clinical improvement: 1) MPT (to measure function), and 2) GFI (to measure patient perception of function). Meaningful clinical improvement will be defined by an increase of at least 4 seconds in MPT or a decrease of at least 4 points in GFI score. Participants will be dichotomized as having meaningful clinical improvement, or not, based on these outcomes. Predictors will include MIP, MEP, maximum SPL, breaths per minute, FVC, FEV1, and P_s. These measures were chosen because they are directly influenced by the integrity of the respiratory system.

Sample Size Justification

We considered maximum phonation time (MPT) as the primary outcome measure for sample size calculation. This measure was chosen because 1) low MPT is a hallmark of patients with presbyphonia, and 2) MPT is directly affected by both the laryngeal and respiratory systems. To estimate the expected effect size between VFE and the I+IVFE and E+VFE groups, we considered MPT values from groups of an

elderly population with different glottal closure and spirometry profiles (49). Considering that a combined intervention (inspiratory or expiratory training combined with voice therapy) would address both laryngeal and respiratory deficits, and that a voice therapy-only intervention would directly address only the laryngeal deficits, we compared MPT between the no-deficit group (complete glottal closure and normal spirometry) and the respiratory-deficit group (complete glottal closure and altered spirometry)(49). Based on these values and the pooled standard deviations, the expected difference between our control and experimental groups would represent a large effect size. As for the withinsubjects effect, a study by Nam et al.(50) found a 33% increase in MPT following a respiratory training intervention program in young adult singers. This corresponds to a very large within-subjects effect size with values of d exceeding 1.2. For Aim 2, we will assess improvement in 2 ways: function (a MPT increase of 4 seconds, which has been associated with a positive perceived effect following voice therapy in older adults(51)) and patient perception of function (a Glottal Function Index (GFI) score decrease of 4 points). An increase of 4 seconds in MPT and a decrease of 4 points on the GFI instrument both correspond to medium-large effect sizes considering the reported standard deviations of these measures in older subjects and in patients with glottal insufficiency (5.1 and 4.5, respectively) (42, 52). Based on the reported studies, the expected effect size for within-subjects and between-subjects differences was set at d=0.90. To have an 80% power to detect an effect size of d=0.90 with an alpha of 0.1 (since this is a pilot study), 15 participants are needed in each group. To account for loss to follow-up (estimated 10% dropouts rate), up to 16 participants will be recruited for each group, 48 patients total.

Based on estimated accrual rates, we calculated an average of one presbyphonic patient per week during the recruitment period of 16 months, for a total 64 participants. We are therefore confident of meeting our sample size goal.

Confidentiality

Protection against the loss of confidentiality will be diminished by 1) completing study aims at one data collection site, 2) minimizing the participants involved to only those needed to accomplish the study aims (see sample size justification above), 3) de-identifying data at the earliest opportunity, and 4) maintaining stored data in locked locations whose access is restricted to members of the study team and on the secure MUSC network.

All data will be entered into a database, linked, and de-identified, and labeled with an alphanumeric identifier. Further use of data will be de-identified. The link between patient identity and alphanumeric identifier will remain confidential in a study team member's locked office in a locked cabinet and on a password protected server (MUSC network). Electronic databases used for this study will be password protected and controlled by the study team. Only the study team will have access to participants' identities. Study staff not directly involved with the patient (e.g., biostatistician) will not have access to the linkage between identifier and subject-identifying information. Identities will be maintained in the general study research folders as identifiers on the signed informed consent forms, HIPPA forms, remuneration forms, and codebook. Once a participant is enrolled, he/she immediately will be identified by an alphanumeric code unrelated to any patient's protected health information. This code will effectively de-identify the participant and be used for unique participant data identification in all databases. Access to the electronic database will have a combination of physical and electronic security protections (firewalls) to prevent unauthorized access to this data. Appropriate back-up routines also will be performed to protect data integrity.

